To avoid the misleading results that can be obtained from small sample sizes, we have now scanned a total of 43 unmedicated, moderately depressed patients with MDD and 25 age- and gender-matched healthy controls, which is about twice the size of most PET studies in psychiatry. Notably, about half the patients were treatment-naïve. $[^{11}C](R)$ rolipram binding in brain was measured using arterial $[^{11}C](R)$ -rolipram levels to correct for the influence of cerebral blood flow. MDD subjects showed a widespread, 18% reduction in $[^{11}C](R)$ -rolipram binding (p=0.0001) that was not caused by different gray matter volumes (Fig 4). Decreased rolipram binding of similar magnitude was observed in most brain areas. Rolipram binding did not correlate with the severity of depressive or anxiety symptoms. These results were the first to demonstrate that brain levels of PDE4, a critical enzyme that regulates cAMP, are decreased in unmedicated individuals with MDD *in vivo*. Furthermore, the results are in line with human postmortem and rodent studies demonstrating downregulation of the cAMP cascade in MDD and support the hypothesis that PDE4 inhibitors—which increase cAMP cascade activity—may have antidepressant effects.

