The purpose of this study is to assess whether uptake in dysplastic bone reflects parent radioligand binding to the enzyme or merely accumulation of radiometabolites, which are expected to have no affinity for the enzyme. For this purpose, we need not administer a receptor saturating dose of roflumilast, as the Lassen occupancy plot has great sensitivity to measure the percentage occupancy and then to extrapolate to 100% occupancy (Cunningham et al., *J. Cereb. Blood Flow & Metab.*, 30: 46-50, 2010). The sensitivity derives from the fact that it is a within subject comparison of multiple regions (in brain or periphery) at baseline and after blockade. We have used the Lassen plot numerous times, including to measure the occupancy of PDE4D subtype by the therapeutic candidate BPN14470. The figure below shows that that the occupancy (i.e., slope) is ~65% and the nondisplaceable uptake (V_{ND} or x-intercept) is ~4.9 mL \cdot cm⁻³.

2. Study Objectives

This study will investigate cAMP signaling in the brains of individuals with MAS using $[^{11}C](R)$ -rolipram PET imaging.

a. Primary objectives

We will study PDE4 levels in patients with MAS by comparing $[^{11}C](R)$ -rolipram binding in various brain regions between patients and age-matched healthy controls. In addition, in whole body imaging of patients with MAS, we will compare $[^{11}C](R)$ rolipram uptake between areas of fibrous dysplasia and adjacent unaffected bones. In whole body scans, we will also compare $[^{11}C](R)$ -rolipram uptake in peripheral organs between subjects with MAS and healthy controls. The reason for doing the latter comparison is that some tissues of MAS may contain the *GNAS* mutations even if there are no obvious structural changes.

b. Secondary objective

In order to quantify the amount of $[^{11}C](R)$ -rolipram binding in patient whole body scans, we will perform a blocking scan with 500 µg roflumilast, a FDA approved PDE4 inhibitor. Because of potential differences in metabolism of $[^{11}C](R)$ -rolipram in in the periphery of healthy controls and patients, it is difficult to interpret whether or not the $[^{11}C](R)$ -rolipram uptake is specific. By performing a blocking scan, we can quantify the amount of specific $[^{11}C](R)$ -rolipram binding to determine if there is a difference between healthy controls and patients.

3. Subjects

a. Description of study populations

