The third outcome measure will be the difference in SUV between the baseline and the blocked whole-body scans. SUV is calculated as stated above.

10. Statistical Analysis

a. Analysis of data/ study outcomes

PET and MRI images will be co-registered for anatomic definition of brain regions. Brain and plasma data will be analyzed with compartmental and graphical modeling to calculate $V_{\rm T}$, which is proportional to the density of receptor or enzyme. $V_{\rm T}$ will be calculated both for regions of the brain and on a voxel basis. PET whole body images will be analyzed by drawing organs and by calculating AUC of SUV. For comparisons between subjects with MAS and healthy controls in brain and peripheral organs, an unpaired test, such as t- and Mann-Whitney tests will be used. In addition, in peripheral organs of MAS, for comparisons of PET data between affected and unaffected organs, a paired test will be applied if the contralateral side is unaffected. If contralateral side is also affected or not available, an unpaired test will be applied to compare the same tissue/organ between patients and healthy controls. For the statistical analyses, SPSS, PMOD, SPM, Freesurfer or equivalent programs will be used.

b. Power analysis

This is an exploratory study focusing on PET imaging. Clinical data obtained under 98-D-0145 may be used to interpret the relationship between PET findings and clinical manifestations of the disease. Although constitutive activation of $G_s\alpha$ is expected to increase cAMP signaling, which increases PDE4 levels, PDE4 levels in MAS are not known in postmortem tissue either in brain or in peripheral organs such as bone. Therefore, we cannot do a realistic power calculation.

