To achieve the goals of this exploratory study, we request a total of 35 subjects: ~10 MAS subjects to undergo brain PET scan, ~10 MAS subjects to undergo whole body PET, and 15 healthy controls to undergo a brain scan and/or a whole body PET scan. By limiting subjects with MAS to those who have craniofacial fibrous dysplasia and neuropsychological symptoms, we expect to increase the likelihood of detecting changes in PET in this small sample size. To limit the number of study participants, all MAS and healthy subjects will be asked if they would be willing to have both brain and whole body PET scans. A smaller number of 15 healthy subjects are requested because healthy subjects are more likely to have both brain and whole body scans. Our previous study of [¹¹C](*R*)-rolipram brain scans in healthy subjects found that the coefficient of variation (SD/mean) of VT was 19%. Based on the activation of G_sa, we hypothesize that MAS patients will show increased rolipram binding for whichever one-sided test is appropriate. Assuming a 20% dropout from 10 subjects (thus, eight subjects per group) plus a 19% coefficient of variation (SD/mean) will provide a power of 0.80 to detect a 19% increase.

11. Human Subjects Protection

a. Subject selection

The study will be open to all racial and ethnic groups and will not target any particular group. Healthy volunteers will be recruited to match the patient group for age. Those who are HIV positive are excluded because the possible viral effects on the brain could interfere with interpretation of the outcome of the study.

b. Justification for exclusion of children

We will exclude children younger than 18 years of age to avoid radiation exposure to minors because the risks of radiation exposure outweighs the benefits.

c. Justification for inclusion of other vulnerable subjects

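### The decision rule for the brain V_T comparison is under-specified (one-sided in 10b, no sidedness in 10a, no alpha anywhere), and the stated power of 0.80 for a 19% increase is not delivered at eight per group.

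*Combined protocol and SAP*

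**What the plan says.** Section 9a makes brain V_T the primary outcome, and section 2a says that binding is compared between patients and controls. Three places bear on how that comparison is tested.

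- **Section 10a (analysis):** for MAS against controls, "an unpaired test, such as t- and Mann-Whitney tests will be used". It gives no sidedness, alpha or confidence level.
- **Section 10b (power):** "we hypothesize that MAS patients will show increased rolipram binding for whichever one-sided test is appropriate". It then assumes eight subjects per group (ten less 20% dropout) and a 19% coefficient of variation, and says that this "will provide a power of 0.80 to detect a 19% increase". No alpha is given here either.
- **Précis, outcome measures:** the investigators expect greater binding in MAS than in controls in brain regions, the same direction as 10b.

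Section 10b also calls the study exploratory. It disclaims a realistic power calculation because "PDE4 levels in MAS are not known in postmortem tissue either in brain or in peripheral organs such as bone".

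**The concern.** An analyst working from 10a alone would probably run a default two-sided test; one who carries 10b across would run a one-sided test. Neither section gives the level. That leaves the rule for the primary outcome to be settled after the data are in hand, at sample sizes where the choice can change the result.

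Sidedness also decides which findings the study can report. A one-sided test for an increase would report any decrease, however large, only as a failure to show an increase. In a first look at brain PDE4 in this disease, that is a real restriction.

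The power statement might be expected to reveal the intended alpha. It does not, because the stated 0.80 matches no conventional level.

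**Working it through.** **Inputs, all from section 10b unless marked**
- n = 8 per group after dropout; about 10 brain scans per group are expected (Précis; section 3a).
- SD = 19% of the mean, from healthy subjects: "the coefficient of variation (SD/mean) of VT was 19" per cent. Equal SDs in the two groups are assumed.
- Target difference = 19%, so the standardised difference is 19/19 = 1.0.
- Stated power = 0.80.
- Alpha is not stated. I take 0.05 and show a range.

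**1. Trying to reproduce the stated power**

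Standard error of the difference: SE = SD × √(2/n) = 19% × √(2/8) = 9.5%.

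Noncentrality: 19/9.5 = 2.00, with 2n − 2 = 14 degrees of freedom.

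Power = P(T > t_crit), where T is noncentral t with 14 df and noncentrality 2.00. The normal version is Φ(2.00 − z_crit).

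| Test, n = 8 per group | Power, t | Power, normal |
|---|---|---|
| One-sided 0.05 | 0.60 | 0.64 |
| Two-sided 0.05 (same as one-sided 0.025) | 0.46 | 0.52 |
| One-sided 0.10 | 0.74 | 0.76 |

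A simulated exact Mann-Whitney test gives about 0.54 at one-sided 0.05 and 0.44 at two-sided 0.05. Solving for the alpha that yields 0.80 gives a one-sided level of 0.133 (t) or 0.123 (normal).

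The only eight-subject variants near 0.80 treat the data as one-sample or paired: 0.815 by t at one-sided 0.05, and 0.807 by the normal formula at two-sided 0.05. Neither is the two-group design.

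**2. What the design does deliver at alpha 0.05 (t-test)**

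| | One-sided | Two-sided |
|---|---|---|
| Power for 19%, n = 8 | 0.60 | 0.46 |
| Power for 19%, n = 10 | 0.69 | 0.56 |
| Difference detectable with 0.80 power, n = 8 | 24.9% | 28.6% |
| Difference detectable with 0.80 power, n = 10 | 22.0% | 25.2% |
| n per group for 0.80 power at 19% | 14 | 17 |

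**3. Where sidedness changes the result (alpha 0.05)**

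Smallest significant observed difference = t_crit × SE.

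- n = 8, 14 df: one-sided 1.761 × 9.5% = 16.7%; two-sided 2.145 × 9.5% = 20.4%.
- n = 10, 18 df, SE = 19% × √(2/10) = 8.50%: one-sided 1.734 × 8.50% = 14.7%; two-sided 2.101 × 8.50% = 17.9%.

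An observed increase between the two limits is significant one-sided only. If the true increase is 19%, the chance of landing there is the difference between the two powers: 0.601 − 0.461 = 0.14 at n = 8, and 0.694 − 0.562 = 0.13 at n = 10.

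For an observed increase of exactly 19%:
- n = 8: t = 19/9.5 = 2.00, p = 0.033 one-sided and 0.065 two-sided.
- n = 10: t = 19/8.50 = 2.24, p = 0.019 one-sided and 0.038 two-sided.
- n = 10, if the MAS SD scales with its mean: two-sided p = 0.057.

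**4. A decrease**

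Take an observed fall of 18%, purely as an illustration. At n = 10, t = −18/8.50 = −2.12, so p = 0.048 two-sided and 0.98 on the one-sided test for an increase. At n = 8, t = −18/9.5 = −1.89, so p = 0.079 and 0.96.

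**The case against.** The best defence is that the plan is coherent as it stands. Section 10a is silent on sidedness and does not say two-sided, so the wording of 10b can be read as the one-sided form of whichever of the two tests named in 10a is used. The direction was stated in advance, in the Précis as well as in 10b, with a mechanistic rationale. The study is labelled exploratory and disclaims a realistic power calculation. All of this stands, and it rules out several stronger readings.

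- **That 10a and 10b contradict each other.** A reader might infer this, but silence in 10a is not a two-sided rule. The secondary objective's wording, "to determine if there is a difference between healthy controls and patients", does not help, because it concerns the roflumilast-blocked whole-body scans and not brain V_T.
- **That the plan's own 19% target is positive or negative depending on the section followed.** This needs alpha near 0.05 and about eight per group. With equal SDs, 19% is significant either way at nine per group (two-sided p = 0.0499) and at ten.
- **That a decrease is to be expected.** The Introduction reports that "MDD subjects showed a widespread, 18% reduction in" rolipram binding, but in unmedicated depression. Section 3c excludes controls with any Axis I history and sets no such exclusion for MAS patients, so some overlap is possible. The neuropsychiatric features that the Introduction lists for MAS do not include depression.

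The defence does not answer the missing alpha. Nor does it rescue the power figure: disclaiming a realistic calculation does not make "a power of 0.80 to detect a 19% increase" correct, and it fails even on the one-sided test that the plan prefers.

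**Conclusion.** The concern holds as an under-specified decision rule together with a power figure that the design does not deliver.

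The power shortfall is the firmer part. At eight per group, 0.80 becomes about 0.60 (one-sided 0.05) or 0.46 (two-sided 0.05), and no conventional alpha recovers it. This rests on the plan's n and coefficient of variation, equal SDs and an unpaired t-test; the simulated Mann-Whitney test does slightly worse.

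The sidedness part is conditional. With alpha 0.05 assumed, the disputed range is 16.7% to 20.4% at eight per group and 14.7% to 17.9% at ten. A reader might infer that the plan rules out declaring a decrease. That follows only if the one-sided test of 10b is also the analysis test, which 10a does not say. It remains worth preventing, since the plan itself says that PDE4 levels in MAS are not known.

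The exploratory label lowers the stakes but does not remove the need for a stated rule and a correct figure.

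**What to change.** **Section 10a:** state that the MAS-versus-control comparison of brain V_T is tested two-sided at 0.05 and reported as a difference with a 95% CI, with an increase as the expected direction.

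**Section 10b:** replace the one-sided wording with that test. Restate the figure as power of about 0.46 for a 19% difference at eight per group (0.56 at ten), or a difference of about 29% detectable with 0.80 power at eight per group.

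**If the sponsor keeps a one-sided 0.05 test:** say so in 10a, and give power of about 0.60, or a detectable increase of about 25%, in 10b.

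The cost is wording and a less favourable stated sensitivity: at eight per group the two-sided test needs an observed difference of 20.4%, against an increase of 16.7% one-sided. No patients, scans or procedures are added. The change does not name a primary brain region; V_T is analysed by region and by voxel, so that choice stays open.

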Study population: Participants will include 20 subjects with MAS and 15 healthy subjects group-matched to MAS subjects for age and gender. Both MAS subjects and healthy controls will have one or two PET scans: one whole body and one brain scan. We expect ~10 brain and ~10 whole body scan to be performed in each group. In addition, subjects who have undergone a baseline whole body scan will be given the option to have a second blocked whole body scan after administration of the PDE4 inhibitor roflumilast.

Design: Subjects with MAS will be recruited from participants in 98-D-0145 "Screening and Natural History of Patients with Polyostotic Fibrous Dysplasia and the McCune-Albright Syndrome" (PI: [name]). Only participants in protocol (98-D-0145) who provided self-consent without a legally authorized representative will be recruited. Brain PET scans will be performed by measuring metabolite-corrected arterial input function. Venous blood sampling will be performed for whole body scans. Subjects willing to undergo a second whole body scan will take 500 µg roflumilast P.O. prior to the scan. Blood sampling will be performed for the second whole body scan.

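### Section 10b claims power 0.80 for the primary brain comparison; its own inputs give about 0.60 in a one-sided two-sample t-test at alpha 0.05

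*Combined protocol and SAP*

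**What the plan says.** The primary outcome is brain V_T, compared between MAS subjects and healthy controls (Précis; section 9a). For that comparison section 10a says that "an unpaired test, such as t- and Mann-Whitney tests will be used".

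Section 10b first calls the study exploratory and says that a realistic power calculation is not possible, because PDE4 levels in MAS are unknown. It then gives one. The inputs are:

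- variability from an earlier study in healthy subjects, where "the coefficient of variation (SD/mean) of VT was 19" percent;
- direction: "we hypothesize that MAS patients will show increased rolipram binding for whichever one-sided test is appropriate";
- size: "Assuming a 20% dropout from 10 subjects (thus, eight subjects per group");
- result: "eight subjects per group) plus a 19% coefficient of variation (SD/mean) will provide a power of 0.80 to detect a 19% increase".

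The group size agrees with the Précis, which says "We expect ~10 brain and ~10 whole body scan to be performed in each group", and with section 3a. No significance level is stated anywhere.

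**The concern.** The effect and the SD are both 19% of the mean, so the standardised difference is exactly 1.0. Eight per group is too few for power 0.80 at that difference in a two-sample comparison at a usual significance level.

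This is the only quantitative support for the number of brain scans, and it concerns the primary outcome. Those who weigh the study's burden (arterial line, radiation, no direct benefit) against what it can show are told that a true 19% increase would be missed one time in five. If the figure is too high, a non-significant V_T result also carries less information than the plan implies, and a reader who relied on 0.80 could take it as evidence against a 19% increase.

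**Working it through.** **Inputs**

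- Test: unpaired, two independent groups (section 10a).
- Side: one-sided (section 10b).
- n per group: 10 × (1 − 0.20) = 8 (section 10b).
- SD: 19% of the mean; difference: 19% (section 10b). Standardised difference d = 19/19 = 1.0.
- Alpha: not stated; 0.05 assumed and varied below.

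**The plan's figure, recomputed.** For a two-sample t-test with n per group, df = 2n − 2 and the noncentrality is d × √(n/2). With n = 8, df = 14 and the noncentrality is 1.0 × √4 = 2.0. The one-sided 5% critical value is 1.761. The probability that a noncentral t with 14 df and noncentrality 2.0 exceeds 1.761 is **0.601**. The normal approximation, Φ(2.0 − 1.645) = Φ(0.355), gives 0.639. Neither is 0.80.

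**Can another reading reach 0.80?** All rows use a true 19% increase.

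| Scenario | Power |
|---|---|
| 8 vs 8, t-test, one-sided 0.05 | 0.601 |
| 8 vs 8, Mann-Whitney, one-sided 0.05 (simulated) | about 0.54 |
| 8 vs 8, CV 19% in both groups, one-sided 0.05 | 0.534 |
| 8 vs 8, log scale, one-sided 0.05 | 0.545 |
| 8 vs 8, t-test, one-sided 0.10 | 0.745 |
| 8 vs 8, t-test, one-sided 0.15 | 0.822 |
| 8 vs 8, t-test, two-sided 0.05 | 0.461 |
| 10 vs 10 (no dropout), one-sided 0.05 | 0.694 |
| 8 vs 15 (all accrued controls), one-sided 0.05 | 0.714 |
| 10 vs 15, one-sided 0.05 | 0.768 |
| 16 vs 12 (all target completers), one-sided 0.05 | 0.817 |

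In the constant-CV row the SD in MAS is 19 × 1.19 = 22.6, the pooled SD is √((19² + 22.6²)/2) = 20.9, and d = 19/20.9 = 0.91.

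Solving for alpha, 8 vs 8 reaches 0.80 at a one-sided alpha of about 0.133.

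**Possible source.** A one-sample or paired t-test with n = 8 has df = 7 and noncentrality 1.0 × √8 = 2.83, which gives 0.815 at one-sided 0.05. This is close to 0.80, and it would arise if the sampling variance of the second group were left out. The documents do not show the method, so this is an inference, and the conclusion does not depend on it.

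**What the design can detect with power 0.80, and what 19% would need (alpha 0.05)**

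- 8 per group: d = 1.308, and 1.308 × 19% = 24.9% one-sided; d = 1.507, and 1.507 × 19% = 28.6% two-sided.
- 10 per group: 22.0% one-sided; 25.2% two-sided.
- For a 19% increase one-sided: 13 per group gives 0.797 and 14 gives 0.824. Two-sided: 17 per group gives 0.807.

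**The case against.** The strongest reply is that the study is labelled exploratory and section 10b itself disclaims a realistic power calculation, so the sentence is only illustrative. No decision rule, stopping rule or test depends on the 0.80, and the group sizes also have practical reasons: limiting the number of participants and allowing both scans in one person. That bears on how much weight the figure carries. It does not make it right: the disclaimer concerns the unknown true effect in MAS, whereas power for a specified 19% increase is arithmetic.

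A second reply is that more people may have brain scans than the sentence assumes. If all 16 MAS and 12 control completers targeted in section 3a did so, power would be 0.817. But the sentence itself uses eight per group, the Précis and section 3a expect about ten brain scans per group, and section 3a expects MAS subjects to be less likely to have both scans.

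Three points on the other side stand. The 0.60 rests on an assumed alpha of 0.05. The plan chose a one-sided test, so 0.60 is the direct comparator and the two-sided 0.46 is only a sensitivity figure. And nothing in the plan says that a null result will be read as excluding a 19% increase; that is a risk of interpretation, not a stated intention.

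**Conclusion.** The stated power is wrong. For the inputs in section 10b and the unpaired test in section 10a, power is 0.60 at one-sided alpha 0.05, 20 percentage points below the figure given. The chance of missing a true 19% increase is about 40% rather than 20%. This assumes normally distributed V_T with the same SD in both groups; the Mann-Whitney, constant-CV and log-scale variants are all lower, at 0.53 to 0.55. The only unstated input is alpha, and it would have to be about 0.13 one-sided to give 0.80. The correction is needed because the figure concerns the primary outcome and is well outside any rounding. It does not undermine the exploratory aim.

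**What to change.** Replace the power sentence in section 10b with one that names the test and the alpha, for example:

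> With eight subjects per group, an SD of 19% of the mean and a one-sided two-sample t-test at alpha 0.05, power is 0.60 for a 19% increase in V_T and 0.80 for a 25% increase; with ten per group, power is 0.69 for a 19% increase and 0.80 for a 22% increase.

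If the sponsor intends another alpha, it should be stated and the figures recomputed; at two-sided 0.05 with eight per group they are 0.46 for a 19% increase and 0.80 for about 29%.

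Add to section 10a that the group difference in V_T will be reported with its confidence interval, so that a non-significant result is not taken to exclude a 19% increase.

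The cost is a sentence or two and a less favourable stated power. No change to enrolment, scans or procedures is needed.
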